1.0 Objectives

1.1 Describe the purpose, specific aims, or objectives of this research.

Response:

Pilot Phase: The purpose of this phase is to conduct taste tests to determine children's reactions to foods that are being considered for the subsequent experimental phase.

Experimental Phase: The objective of this research is to make healthier kids' meal options more appealing and easier to choose via an in-restaurant intervention that combines repeated exposure and choice architecture strategies. This phase has 2 main aims:

Aim 1: To test effects of a healthier kids' meal intervention on children's meal orders.

Aim 2: To test effects of a healthier kids' meal intervention on children's dietary intake.

1.2 State the hypotheses to be tested, if applicable.

NOTE: A hypothesis is a specific, testable prediction about what you expect to happen in your study that corresponds with your above listed objectives.

Response:

Pilot Phase: There is no explicit hypothesis during this exploratory pilot phase.

Experimental Phase:

Hypothesis 1a: 4-to-8-year-old study participants in intervention restaurants will be more likely than controls to select one of the promoted healthier kids' meals at post-test.

Hypothesis 1b: 4-to-8-year-olds in the intervention group will order fewer calories and desserts and less saturated fat, sodium and sugar at post-test versus controls.

Hypothesis 1c: The promoted healthier meals will make up a greater percentage of kids' meals ordered in intervention restaurants versus controls, based on sales data across the study period.

Hypothesis 2: Compared to controls, 4-to-8-year-old study participants in the intervention group will consume fewer calories and less saturated fat, sodium, and sugar in the restaurant at post-test.

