4.0 Study Design

4.1 Describe and explain the study design (e.g. case-control, cross-sectional, ethnographic, experimental, interventional, longitudinal, observational).

Response:

Pilot Phase: A cross-sectional study design will be used. About 25 children from 1-3 restaurant locations will participate in taste tests to inform food selections for the subsequent experimental phase. Families will be asked if they want to

participate in taste tests during a regular visit to a location of the study restaurant (Anderson's Frozen Custard). Participating children will taste up to 5 side dishes (e.g. applesauce, carrot sticks, mandarin oranges) and up to 5 main dishes (e.g. turkey sandwich, peanut butter and banana sandwich). They will then use a visual face scale to rate their liking and rank ordered preferences for presented options and be asked for their opinions on the foods (e.g., why they liked/disliked the food items). Parents will be asked to complete a brief demographic survey on an electronic tablet or with pen and paper.

Experimental Phase: A cluster-randomized design will be used. 6 locations of Anderson's, a regional quick-service restaurant in the Buffalo, New York, area will be paired based on income levels in the surrounding census tracts. A location from each pair will be randomized to each study group (intervention, control). Recruitment and data collection will be conducted across about 3 to 5 cohorts, with recruitment conducted either in person or remotely during a family's regular visit to Anderson's.

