In both phases, we will recruit within the restaurant locations and via advertisements on the restaurant's social media platforms, either in-person or remotely, with approval of the restaurant owner as well as the managers of the specific restaurant locations. With regards to social media, the study will be advertised via Facebook/Instagram using Anderson's social media account only. The advertisement to be uploaded to Facebook is attached. We believe recruiting a sample of about 25 (pilot phase) and 930 families (experimental phase) with 4-to-8-year-old children will be feasible based on our conversations with the restaurant owner about typical traffic, naturalistic observations and past research in Anderson's restaurant locations, and our past experience conducting research in restaurants generally. We have allocated about 3-4 months of recruitment time across the 3 – 5 cohorts in the experimental phase, with a plan to study 2 restaurant locations per cohort. This timeline was informed by prior observations indicating that about 10 families eat at Anderson's per evening as well as the fact that we were able to recruit 120 participants from 1 location of Anderson's over 2 months in our past research. The prior observation suggests the possibility of about 3600 families being present in the restaurant during the recruitment period

across cohorts, which is greater than the anticipated 2300 families who will need to be screened, as indicated above.

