9.0 Recruitment Methods

☐ N/A: This is a records review only, and subjects will not be recruited. NOTE: If you select this option, please make sure that all records review procedures and inclusion/exclusion screening are adequately described in other sections.

9.1 Describe when, where, and how potential subjects will be recruited.

NOTE: Recruitment refers to how you are identifying potential participants and introducing them to the study. Include specific methods you will use (e.g. searching charts for specific ICD code numbers, Research Participant Groups, posted advertisements, etc.).

Response:

For both phases potential subjects will be recruited at participating Anderson's restaurants, either in person or remotely. We aim to begin recruiting for the pilot phase around November 2019 and for the experimental phase around May 2022, following IRB approval.

Pilot Phase: Study staff will approach families with at least one child who might plausibly be in the target age range (4-8 years) after they have placed their order and will invite them to join a study where they can taste test different main dishes and sides. Those interested will complete screening questions and will be provided with consent forms as described herein.

Experimental Phase: Recruitment will be conducted across approximately 3 – 5 cohorts. Families will be informed that study participation involves 7 more visits to the Anderson's location where they were recruited, 6 of which will be during an exposure period lasting about 2 months. Families entering study restaurants will be invited to join a study with incentives including earning a free kids' meal at Anderson's. Families will also be recruited via advertisements from Anderson's social media account on Facebook. The ad that will be used is attached and will be uploaded to Anderson's Facebook page, directing them to contact the study team for more information and screening.

Those interested will complete screening questions and will be provided with consent forms to complete on paper or online and will be given adequate time to ask any questions they may have. Initial/baseline data will then be collected and will include experiences during that initial restaurant visit, as described herein.

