upcoming opportunity for children to redeem the token that comes with all kids' meals at this restaurant for a toy instead of a dessert. Families recruited into the study will also receive paper or electronic frequent diner cards (see attached Sample Marketing Materials_Punch Card). In the intervention group, participating children must order a featured healthier meal 6 times during the exposure period to earn a free kids' meal. Information about the two featured meals will appear on the cards. Restaurant staff will validate the cards when a target meal is purchased and the card is presented (e.g., by marking an image of the meal using a novelty stamp when that meal is purchased and a paper card is presented or by scanning the image when an electronic frequent diner card is presented). Control group cards will be similar but can be used during purchases of any kids' meal. When either card is marked, the child will also receive a small prize (e.g., sticker). Restaurant staff will be trained to know which items come with the two featured meals, to allow use of the intervention group's healthy frequent diner cards only for purchases of those meals, and to only allow one purchase per card per visit.

Exposure Period (about 2 months per cohort). Participating families will return to the Anderson's location where they were recruited on a weekly basis during an exposure period lasting about 2 months (they will be asked to visit at least 6 times during this period). Placemats will be available at the restaurant entrance, and signage with corresponding information will be displayed. In intervention restaurants, the placemats and signs will advertise promoted meals and the opportunity for children to redeem their "dessert" token for a toy. In intervention restaurants, boxes of small assorted toys (e.g., yo-yo, action figure, mini puzzle) will be available. This opportunity will not be advertised in control restaurants, but we will offer to provide them with toys in case a customer should request one.

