Experimental Phase: Orders. At initial and post-assessment time points, researchers will ask the participating parent to identify all items ordered for and eaten by the child that day and will record: 1) whether or not one of the healthier featured kids’ meals was ordered, and 2) the specific main dish(es), side dish(es), beverage(s), and dessert(s) ordered for/ eaten by the child, noting whether each item was shared, taken to go, or was finished in the restaurant. Total calories, saturated fat, sugar, and sodium ordered for the child will be calculated using nutrition information available from the restaurant. At post-test, families’ frequent diner cards will also be photographed or collected (if paper version) or confirmed via our electronic records (if electronic version). Researchers will record the number of marks/punches on the card, and in the intervention group, which of the healthy meals the marks correspond to. Questions about orders will also be asked via online survey at midpoints (see attachments). For those participating in the remote data collection, orders will be collected at all of these same time points via online surveys sent to participants’ electronic devices.

Sales Data. We will collect aggregated sales data from the restaurant to monitor sales of kids’ meals across all patrons in Anderson’s restaurants during the recruitment, exposure, and redemption periods and parallel time points one year prior. These data are aggregated and de-identified and do not require IRB approval; therefore, the sales data are not described further herein.

Dietary Intake at the Restaurant. Children’s dietary intake will be measured using plate waste methodology, a gold standard for measuring dietary intake. Study staff will ask the parent which items were ordered for and consumed by the target child, recording the names of the items, and will collect all uneaten food and

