17.0 Data Management and Analysis

17.1 *Describe the data analysis plan, including any statistical procedures. This section applies to both quantitative and qualitative analysis.*

Response:

Pilot Phase: Child feedback will be used to determine which food components will be used in the experimental phase.

Experimental Phase: Descriptive statistics, normality plots, and study group differences will be examined for all variables, with results informing analyses (e.g., using non-parametric statistics if appropriate). Planned analyses corresponding to each aim are described below. Analyses incorporate random effects for restaurant location as required in cluster-randomized trials.

Aim 1. A mixed model with a binomial distribution will test whether intervention children are more likely to order a healthier promoted meal compared to controls,

with study group, time point (initial, mid1-mid6, and post), and the group-by-time interaction as fixed effects, a random effect for restaurant location, and a contrast focused on study group differences at post. Mixed models with linear distributions will compare the groups on calories, saturated fat, sodium, and sugar ordered, with the same factors. We will use sales data and chi-square analyses to compare the percentage of kids' meals ordered that were healthier featured meals in intervention versus control restaurants across the study period and separately by recruitment, exposure, and redemption periods. We will also summarize child and parent orders at each time point and the frequency of behaviors of interest (e.g., who ordered for the child) during parent-child interactions in intervention and control groups and will compare the number of kids' meals ordered in each group of restaurants against initial sales data from parallel time periods one year prior, overall, by cohort, and by recruitment, exposure, and redemption periods.

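### The prior-year sales comparison sets each arm against its own past with no between-arm contrast, so it cannot separate an intervention effect from changes both arms share (minor)

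*Combined protocol and SAP*

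**What the plan says.** The combined protocol and SAP plans two uses of the aggregate restaurant sales data, both in section 17.1 under Aim 1.

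- **Featured-meal share, between arms.** Chi-square analyses will "compare the percentage of kids' meals ordered that were healthier featured meals in intervention versus control restaurants across the study period". This serves Hypothesis 1c in section 1.2: "The promoted healthier meals will make up a greater percentage of kids' meals ordered in intervention restaurants versus controls".
- **Total kids' meals, against the previous year.** The other planned step is to "compare the number of kids' meals ordered in each group of restaurants against initial sales data from parallel time periods one year prior". It is done for the whole study and repeated within each cohort and each study period. It closes a sentence that begins as a descriptive summary. No test, model, alpha or hypothesis is attached.

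Section 10.2 says sales are collected "during the recruitment, exposure, and redemption periods and parallel time points one year prior". Table 1 lists restaurant-wide kids' meal orders under the primary Orders heading, but the endpoints in section 2.1 do not include total kids' meals sold.

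The restaurants "will be paired based on income levels in the surrounding census tracts" (section 4.1), one of each pair is randomised to each arm, and section 10.1 assigns each pair to a cohort. In both arms, families get a frequent diner card (any kids' meal counts on control cards), "they will be asked to visit at least 6 times during this period", and are paid $5 per marked exposure up to 6 (section 10.1).

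**The concern.** Setting an arm against its own past is an uncontrolled before-after comparison. It absorbs whatever changed between the two years, and the documents point to two changes common to both arms:

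- **Study-generated visits.** The cards, the requested visits and the payments apply in intervention and control restaurants alike, and did not exist in the comparison year.
- **Calendar trend.** Section 9.1 plans recruitment "for the experimental phase around May 2022, following IRB approval", so the earliest cohort would be compared with about 2021; section 19.5 gives May 2021, which would make it about 2020. The protocol itself plans for COVID-19 disruption. Later cohorts have later comparison years.

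What is at stake is interpretation. A rise in the intervention restaurants could be reported as an effect of the promotion. A clear rise in one arm and not the other could be reported as an arm difference. Neither is a test of the intervention, and repeating the comparison by cohort and period multiplies the occasions. The randomised controls that would remove shared changes are available for every pair, but the plan does not say they will be used for that.

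**Working it through.** The plan gives no figure for this comparison, so there is none to reproduce.

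**1. What is estimated.** Let S be the year-on-year factor shared by both arms and θ the intervention's effect on kids' meal volume. The expected study-year to prior-year ratio is S × θ in intervention restaurants and S in controls. The comparison as written reports these two quantities separately. With θ = 1 and S ≠ 1, both move. Only the quotient (S × θ)/S = θ isolates the intervention.

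**2. How large S might be in the exposure period.** Inputs from the documents: 465 families per arm, and 684 of 930 retained if the planning figures hold (section 17.2); at least 6 visits (section 10.1); and "prior observations indicating that about 10 families eat at Anderson's per evening" (section 5.3).

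- Requested visits per arm: 465 × 6 = 2,790. With retention: 465 × 684/930 = 342, and 342 × 6 = 2,052.
- Prior-year volume is not given. *Assumed:* 10 families × 60 evenings × 3 restaurants × one kids' meal = 1,800 per arm, with a range up to 18,000. Section 5.3 does not say that the 10 families are per location.
- If 10% of requested visits are extra to usual custom: 205/1,800 = 11% to 279/1,800 = 16%. If all are extra: 2,052/1,800 = 114% to 2,790/1,800 = 155%. At 18,000, all 2,790 would be 16%.

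**3. How often a count test would flag a change with θ = 1.** The plan names no test, so this is illustrative. Using P = Φ(extra/√(2 × base + extra) − 1.96), with one extra visit per family (465 meals):

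- base 1,800: 465/√4,065 = 7.29, P = 1.00
- base 5,400: 465/√11,265 = 4.38, P = 0.99
- base 18,000: 465/√36,465 = 2.44, P = 0.68

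**4. Simulation.** 20,000 runs, three restaurants per arm, Poisson counts, 1,800 prior-year meals per arm, θ = 1. The within-arm test is a z test on the log ratio of totals. The between-arm test is a t test on restaurant-level log ratios (4 df). The exactly-one-arm column is 2 × (given arm − both).

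| Shared change | Restaurant-year noise (log SD) | Given arm flagged | Both flagged | Exactly one flagged | Between-arm test rejects |
|---|---|---|---|---|---|
| 0 | 0 | 4.9% | 0.2% | 9.4% | 5.0% |
| +5% | 0 | 31.5% | 10.1% | 42.8% | 4.8% |
| +10% | 0 | 83.6% | 69.9% | 27.4% | 4.9% |
| +20% | 0 | about 100% | about 100% | about 0% | 4.8% |
| 0 | 0.05 | 13.8% | 1.9% | 23.8% | 5.0% |
| +10% | 0.05 | 76.2% | 58.0% | 36.4% | 5.0% |

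The between-arm contrast stays at 4.8% to 5.2% for shared changes from 0% to +50%. At a shared +5% or +10%, a change flagged in one arm only is common although the arms do not differ.

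**5. Precision of the paired contrast.** With 600 prior-year meals per restaurant, no shared change and noise SD 0.05, the variance of one restaurant's log ratio is about 1/600 + 1/600 + 0.0025 = 0.0058. For a pair it is 0.0117 (SD 0.108). On 2 df the 95% half-width is about 4.303 × 0.108/√3 = 0.27, a factor of exp(0.27) ≈ 1.31 either way.

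**The case against.** The strongest reply is that little rests on this comparison. No test is named, the sentence opens as a summary, and the sales hypothesis (1c) has its own between-arm analysis. That stands, and it sets the severity.

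Four stronger readings might be inferred, and the documents do not support them.

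- *That the comparison will show a change in both arms whatever happens.* It needs a shared change. Without one, both arms are flagged in 0.2% of runs, or 1.9% with restaurant-year noise. Section 24.1 argues that participants' costs will not differ from usual, which implies few extra visits. That is not conclusive: section 6.1 requires only 2 to 3 restaurant meals a month at any restaurant, or 4 to 6 in two months, so a family at that threshold would have to bring all of them to this one location for none to be extra there.
- *That the result is unrelated to the intervention.* Promotional signs, placemats and the toy offer could change kids' meal volume, and that would enter the intervention count. The comparison is confounded, not uninformative by construction.
- *That the control restaurants are ignored.* Both arms' changes will be reported, and a by-cohort breakdown places pair members side by side. What is missing is the contrast between them.
- *That the previous year is the only baseline.* Recruitment-period sales precede the in-restaurant signs and are also analysed separately.

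**Conclusion.** The point holds as a minor one. As written, the prior-year comparison cannot distinguish an intervention effect on kids' meal volume from anything both arms share, and the design gives specific reasons to expect a shared change. If there is one, both arms can show a rise with no intervention effect.

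The conclusion rests on the wording of section 17.1 and the features common to both arms. It does not rest on the percentages above, which depend on an assumed base volume, one kids' meal per family, 60 evenings, assumed noise, an assumed share of extra visits and a test the plan does not name. The COVID-19 part concerns the earliest cohort, and the documents give no sales figure for any year. Nothing here affects the analysis of Hypothesis 1c.

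**What to change.** Amend the Aim 1 paragraph of section 17.1 as follows.

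1. For each matched pair and period, compute the study-year to prior-year ratio of kids' meal counts in the intervention restaurant, divided by the same ratio in its control partner.
2. Report the three log ratios, their mean and a 95% interval on 2 df. If a pair is studied in more than one cohort, average within the pair first, so that three independent values remain.
3. Do the same for featured-meal share if prior-year data allow; meals not sold in the earlier year would rule this out.
4. Label within-arm year-on-year changes as descriptive and not as evidence of an intervention effect.

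The cost is wording only, since sales are already collected for all restaurants and both years. The downside is a wide interval from three pairs (step 5 of the working), which is the honest precision of this comparison.

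One limit should be stated with it. Shared proportional changes cancel exactly, but a shared number of extra meals cancels only if pair members sell similar volumes, and pairs were formed on area income. For example, 465/3 = 155 extra meals on assumed bases of 600 and 1,200 give (755/600)/(1,355/1,200) = 1.11 with no intervention effect. Because allocation within pairs is random, this adds to the spread of the three values and does not favour one arm systematically.

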Compensation. Participating families can receive up to \$300 for participating in the study (\$265 for all standard assessments; plus an additional \$35 if in the observed subsample). Families will receive up to \$50 for completing measures at the initial time point. Then, throughout the exposure period (midpoint), they can receive up to \$120: \$90 of the \$120 will be provided during the exposure period for completion of weekly online surveys (divided up and paid weekly), and an additional payment will be provided later for each of the weekly exposures indicated on their frequent diner card ($\$5 \times \text{number of exposures}$, max = 6; determined upon collection of the card at post-test). After the midpoint assessments, families will receive one more payment; this payment will be administered following post-test and will include up to \$50 for completion of in-restaurant post-test measures (final survey; intake measures used during their cohort – i.e., weighed plate waste and/or remote food photography), plus a \$20 bonus for following post-test procedures as instructed (i.e., turning in their frequent diner card at post-test if paper version; coming to originally-scheduled appointment time if in-person), \$25 for completion of the online dietary intake survey (ASA24), and the aforementioned midpoint payments from frequent diner card use. Families will also receive their free kids' meal at post-test if frequent diner cards are completed, and those randomly selected to be included in the observed subsample will receive an additional \$35. Children will receive a small prize (e.g., stickers) each time their frequent diner card is used. Payments will be made via a prepaid debit card provided by the study.

[figure not shown]

Figure 1. Data collection timeline for an individual cohort with main measures. These procedures will happen repeatedly over about 3-4 years to collect data from about 3-5 cohorts.

10.2 Describe what data will be collected.

NOTE: For studies with multiple data collection points or long-term follow up, consider the addition of a schedule or table in your response.

Response: Data collected are detailed below. In addition, please see attachments for corresponding forms/surveys with specific questions to be administered.

Pilot Phase: We will collect data on children’s liking of and preferences for the foods they taste during taste tests, as well as parent-reported demographics.

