Aim 2. We will use mixed models with linear distributions to compare study groups on calories, saturated fat, sodium, and sugar consumed in the restaurant, with study group, time point (initial, post), and the group-by-time interaction as fixed effects and a random effect for restaurant location. We will repeat these analyses using data from repeat 24-hour dietary recalls to examine intervention effects on daily energy, saturated fat, sodium, and sugar intake among participating children (post-test only). We will also explore associations between ordering of the promoted meals and children's dietary intake within the meal and total day and will repeat aforementioned models testing intervention effects on orders and intake, incorporating child sex, age, and weight status (overweight/obese vs. normal weight) as potential covariates and effect moderators. We will also plan ancillary analyses that explore dining at Anderson's locations besides the assigned location and number of exposures as additional factors in the mixed models described above; if there are substantial missing data on number of exposures, we can treat this variable as categorical with "missing" retained as a category, to retain our sample size. Finally, if substantial demographic differences between groups are revealed, we will incorporate propensity scores into our analyses to account for this potential source of bias. Analyses will incorporate multiple imputation methods as appropriate, depending on the extent of missing data.

17.2 If applicable, provide a power analysis.

NOTE: This may not apply to certain types of studies, including chart/records reviews, survey studies, or observational studies. This question is asked to elicit whether the investigator has an adequate sample size to achieve the study objectives and justify a conclusion.

Response:

Pilot Phase: No power analysis is required for this qualitative exploratory phase.

Experimental Phase: To determine the sample size needed to test effects on orders of healthier meals, we used findings from our preliminary research, showing that 27.8% of participants exposed to study placemats and 6.7% of the control group ordered the featured healthier entrees (1). Using these values, an alpha of .05,

power of 80%, 6 cluster, and an intraclass correlation of .01 based on prior restaurant research (2), it is estimated that 124 participants will be needed to test intervention effects on meal selection.

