25.0 Compensation for Participation

25.1 *Describe the amount and timing of any compensation to subjects, including monetary, course credit, or gift card compensation.*

Response:

Pilot Phase: Families will receive \$10 in cash for participating and children will receive a small prize like a sticker.

Experimental Phase: Participating families can receive up to \$300 for participating in the study. Families will receive up to \$50 for completing measures at the initial time point. Then, throughout the exposure period (midpoint), they can receive up to \$120: \$90 of the \$120 will be provided during the exposure period for completion of weekly online surveys (divided up and paid weekly), and an additional payment will be provided later for each of the weekly exposures indicated on their frequent diner card (\$5 x number of exposures; determined upon collection of the card at post-test).

After the midpoint assessments, families will receive one more payment; this payment will be administered following post-test and will include up to \$50 for completion of in-restaurant post-test measures, plus a \$20 bonus for following post-test procedures as instructed (i.e., turning in their frequent diner card at post-test if paper version; coming to originally-scheduled appointment time if in-person), \$25 for completion of the online dietary intake survey (ASA24), and the aforementioned midpoint payments from frequent diner card use. Families will also receive their free kids' meal at post-test if frequent diner cards are completed,

and those in the observed subsample will receive an additional \$35. Children will receive a small prize (e.g., stickers) each time their frequent diner card is used. Payments will be made via U.S. Bank Card.

Payments for the remote cohort will parallel those for the in-person cohort, although the total will be slightly less (\$265) due to measures that cannot be completed remotely and the goal to pay all participants equitably for the completion of the same measures.

- ☐ N/A: This study is not enrolling subjects, or is limited to records review procedures only. This section does not apply.
- ☐ N/A: There is no compensation for participation. This section does not apply.

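### If the exposure factor is the diner-card count, it counts featured meals in one arm and any kids' meal in the other, so the exposure-adjusted group effect on meal orders cannot be interpreted

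*Combined protocol and SAP*

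**What the plan says.** - **Section 17.1, Aim 2.** Ancillary analyses will explore dining at other locations and "number of exposures as additional factors in the mixed models described above". The term is not defined there. The fallback reads "if there are substantial missing data on number of exposures, we can treat this variable as categorical with" a separate level for missing values.
- **Sections 10.1 and 25.1 (compensation).** Payment is made for "weekly exposures indicated on their frequent diner card", and Section 25.1 ties the same phrase to the card: "number of exposures; determined upon collection of the card at post-test".
- **Section 10.1 (cards).** Restaurant staff are trained "to allow use of the intervention group's healthy frequent diner cards only for purchases of those meals". By contrast, "Control group cards will be similar but can be used during purchases of any kids' meal".
- **Section 10.2 (Orders).** The number of marks is recorded in both arms, but the meal behind each mark only in one: "in the intervention group, which of the healthy meals the marks correspond to".
- **Section 17.1, Aim 1.** The order model uses eight time points (initial, six midpoints, post), with group, time and their interaction, and a contrast at post.

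Nothing in the plan puts the count on a common basis or restricts it to use within one arm.

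**The concern.** A model with study group and card marks compares children at the same number of marks. Four marks in the intervention arm mean that the child chose a featured meal four times. Four marks in the control arm mean that the child came four times and had some kids' meal. These are different children, so the group coefficient no longer measures the intervention.

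Two features make this worse. Marks accrue after randomisation and depend on the intervention. And in the intervention arm the mark total is close to the sum of the six midpoint outcomes in the Aim 1 model, so the outcome enters as its own predictor in one arm only.

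At stake is the reading of an exposure analysis in a trial whose added component over the earlier placemat pilot is repeated exposure (Section 3.1). The error favours the intervention.

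**Working it through.** The plan gives no figure for the exposure-adjusted analysis. The yardstick is its planning effect: 27.8% − 6.7% = 21.1 points (Section 17.2).

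**Inputs.** Six marking opportunities (Section 10.1 asks for at least six visits and allows one purchase per card per visit). Featured-meal rate μ from 6.7% to 27.8% (Section 17.2), with 17% in between. Assumed: attendance a = 78% per week; each attended visit earns a control child a mark; a child's own rate follows a Beta distribution with mean μ and concentration c. The correlation between two orders by the same child is then 1/(c+1): 0 (none), 0.05 (mild, c = 20), 0.2 (moderate, c = 4) or 0.5 (strong, c = 1). The documents give no value for attendance or c.

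**Null.** Both arms order alike at every time point, so the unadjusted difference is 0. In a linear model,

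adjusted difference = 0 − b × (mean marks, intervention − mean marks, control) = b × 6a(1 − μ),

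where b is the pooled within-cell slope of ordering on marks.

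**Post-test-only model.** With v = μ(1 − μ)/(c + 1):

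- b = 6av / (V_I + V_C)
- V_C = 6a(1 − a)
- V_I = 6[aμ − a²(μ² + v)] + 36a²v

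For μ = 0.17, c = 4: v = 0.0282, 6av = 0.1321, V_I = 1.2052, V_C = 1.0296, so b = 0.1321/2.2348 = 0.0591. The gap in marks is 4.68 × 0.83 = 3.884. The false difference is 0.0591 × 3.884 = 0.230.

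**All-time-point model, no differences between children.** With q = aμ, and midpoint orders observed only in attended weeks:

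- numerator of b: 6aμ(1 − μ)
- denominator, intervention: 12q(1 − q) + 6a[μ(1 − μ) + 5q(1 − q)]
- denominator, control: 12a(1 − a) + 30a²(1 − a)

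For μ = 0.17: b = 0.6603/(4.732 + 6.075) = 0.0611, and 0.0611 × 3.884 = 0.237.

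False difference at post, in percentage points:

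| Rate μ | Gap in marks | Post only: none | mild | moderate | strong | All time points: none |
|---|---|---|---|---|---|---|
| 6.7% | 4.37 | 0 | 4.4 | 16.4 | 33.7 | 15.7 |
| 17% | 3.88 | 0 | 6.6 | 23.0 | 42.6 | 23.7 |
| 27.8% | 3.38 | 0 | 6.8 | 22.8 | 40.9 | 24.4 |

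Simulation of the same null gave 4–7, 17–24 and 34–43 points post-only and 16–24 with all time points, agreeing with the formulas to about a point.

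**Sensitivity.** Attendance matters. The last column becomes 9 to 16 points at 60% and 28 to 37 at 90%. In simulations at 342 per arm (half of the plan's 684):

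- A logistic all-time-point model without differences between children (rates 6.7–20.6%, attendance 75–80%, restaurant effect omitted) gave odds ratios of 0.98–1.00 unadjusted and 4.2–11.9 adjusted, with false-positive rates of 99–100%.
- A linear mixed model on the initial and post visits, with a restaurant random effect (rate 17%, c = 4, attendance 75%), gave 22 points.
- Calories consumed, taking the 83.3 kcal gap in Section 17.2 (556.6 − 473.3), moved by about −2 to −18 kcal, with 6–14% rejection.

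**Common definitions (rate 17%, c = 4).** An any-kids'-meal count in both arms gave −0.1 to 0.2 points and about 4% false positives. A featured-meal count in both arms gave 0.1 points if exposure-period ordering is equal. It gave −11 points with 97% rejection if the intervention raises ordering during exposure (log-odds +2) but not at post, because the count is then a mediator.

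**The case against.** **The definition and the model are inferred.** Section 17.1 does not say card marks. The link comes from the payment text, and the weekly surveys also track visits and meal selection in both arms. The analysis is ancillary, and the plan does not say that an adjusted group effect will be interpreted. This stands as a condition on the finding. But card marks are the only meaning the plan gives the term, and the models to be extended are the between-arm ones.

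**The size depends on assumptions.** This stands. In a post-test-only model the bias vanishes when children do not differ in liking. If the intervention raises ordering during exposure only, the false difference there falls to 4–18 points (moderate differences, 75% attendance, log-odds shifts of 1 to 3). No single figure should be quoted. The all-time-point model is biased even without differences in liking.

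**Stronger readings that a reader might infer, which the documents do not support:**

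- That the intake results are badly distorted. The effect computed for calories consumed is small.
- That this is the trial's only evidence on repeated exposure. Aim 1 models orders over the six midpoints, and the intervention combines exposure with choice architecture.
- That the missing category would consist largely of families who did not return. Section 10.2 lets electronic cards be confirmed from study records, the fallback is conditional, and Section 17.1 already foresees multiple imputation.

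**Conclusion.** Wrong as written, within an ancillary analysis, if number of exposures carries the meaning it has elsewhere in the plan. A mark-adjusted group effect on meal orders is then not interpretable and can show a benefit about as large as the 21.1-point planning effect when there is none. The size rests on assumed attendance, ordering rates and differences between children, so it is best stated as the ranges above.

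A reader might infer that the trial's main result is compromised. It is not: the contrast at post in Section 17.1 does not contain the exposure factor, and the unadjusted difference stays at about 0 in the null simulations. The sponsor should correct this before the analysis.

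**What to change.** 1. State in Section 17.1 that card marks will not enter the between-arm models and that no mark-adjusted group effect will be interpreted.
2. Analyse exposure within arm. In the intervention arm, report the association of card marks with post-test orders and intake, labelled non-causal. Marks there already count featured-meal purchases validated by restaurant staff, so parent report need not replace them. Use the midpoint surveys as a check.
3. Handle missing counts by multiple imputation, with the midpoint surveys as auxiliary data, instead of a missing category.
4. If a between-arm exposure factor is wanted, define it identically in both arms, for example exposure-period visits with any kids' meal from the midpoint surveys. Label it exploratory, because it is still post-randomisation. A featured-meal count in both arms is not a safe substitute.

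Cost: SAP wording, a little extra coding, and reliance on parent report for any common count. No new data collection is needed.
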